6.16. General Investigational Device Management

6.16.1. Device Accountability

A device accountability log for the TIES® Port and all appliances used shall be kept for this study. Lot numbers must be included in the accountability log. A copy of the completed accountability log will be kept on site for traceability for all subjects, including early terminations. Access to device is restricted to delegated staff in the investigation. Unused and expired devices will be returned to Sponsor at the end of the investigation.

6.16.2. Explant Procedure (if applicable)

If the TIES® Port must be removed, it can be done using standard surgical procedures.

Should there be a reason for explanting the implant and/or the surrounding tissue, it shall be removed in a manner that causes minimal damage to both the implant and the tissues. It is particularly important that implant surfaces and adjacent tissues are kept intact.

See the Surgical Procedure Manual (Appendix) for further detail.

Information on the explant procedure must be documented in source notes and captured in the Case Report Form on "Explant procedure".

All explanted devices must be immediately put into neutral buffered 10% formalin for tissue fixation and returned to the sponsor OstomyCure for evaluation.

6.17.2. Withdrawal

Subjects may withdraw from the study at any time, with or without reason and without prejudice to further treatment. Withdrawn subjects will not undergo any additional study follow-up. The reason for withdrawal will be recorded (if given) in all cases of withdrawal. The investigator may discontinue a subject from participation in the study if the investigator feels that the subject can no longer fully comply with the requirements of the study or if any of the study procedures are deemed potentially harmful to the subject. No new data will be collected after withdrawal from the study. Data that have already been collected on withdrawn subjects will be retained and used for analysis, unless disallowed by national or local regulations.

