5.3.4. Withdrawal

Early termination of study participation will be documented for patients that have signed an informed consent form and who exited for any of the following reasons:

- Subject for whom the implantation procedure has been attempted but cannot completed, for example, due to technical reasons. (These subjects will be followed for six months.)
- Subject who are explanted. (These subjects will be followed for six months.)
- Subject no longer wishes to continue with the study follow-up. No further follow up applies.
- Investigator believes it is the best medical interest of the subject to discontinue study participation due to safety reasons. (These subjects will be followed until study procedure related adverse events have resolved.)
- Death of the subject.

No additional subjects will be recruited to compensate for subjects who withdraw or are withdrawn from the study.

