6.17.3. Unplanned pregnancy

In the event that any subject becomes pregnant during the study, the pregnant subject will be withdrawn from the study. The optimal way to handle the implant will be reviewed on a case by case basis involving the investigator, obstetrician and the subject. No new data will be collected after withdrawal from the study. Data that have already been collected on

CLINICAL INVESTIGATION PLAN

withdrawn subjects will be retained and used for analysis, unless disallowed by national or local regulations.

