8.1. Definitions

Adverse Event (AE):

Any untoward medical occurrence, unintended disease or injury, or untoward clinical signs (including abnormal laboratory findings) in subjects, users or other persons, whether or not related to the investigational medical device

NOTE 1 This definition includes events related to the investigational medical device or the comparator.

NOTE 2 This definition includes events related to the procedures involved.

NOTE 3 For users or other persons, this definition is restricted to events related to investigational medical devices.

Treatment emergent adverse events are adverse events with onset at or following the implantation procedure for the purpose of this study.

Serious Adverse Event (SAE):

Adverse event that:

a) led to death,

b) led to a serious deterioration in the health of the subject, that either resulted in

- 1) a life-threatening illness or injury, or
- 2) a permanent impairment of a body structure or a body function, or
- 3) hospitalization or prolongation of existing hospitalization, or
- 4) medical or surgical intervention to prevent life-threatening illness or injury or permanent impairment to a body structure or a body function,

c) led to foetal distress, foetal death or a congenital abnormality or birth defect

NOTE Planned hospitalization for a pre-existing condition, or a procedure required by the Clinical Investigation Plan, without serious deterioration in health, is not considered a serious adverse event.

CLINICAL INVESTIGATION PLAN

Device Deficiency:

Inadequacy of an investigational medical device related to its identity, quality, durability, reliability, safety or performance. This may include malfunctions, use error, or inadequacy in the information supplied by the manufacturer.

Adverse Device Effect (ADE):

Adverse event related to the use of an investigational medical device

NOTE 1 This definition includes any adverse event resulting from insufficiencies or inadequacies in the instructions for use, the deployment, implantation, installation, operation, or any malfunction of the investigational medical device.

NOTE 2 This definition includes any event resulting from a use error or from intentional misuse of the investigational medical device.

Serious Adverse Device Effect (SADE):

Adverse device effect that has resulted in any of the consequences characteristic of a serious adverse event

Unanticipated Serious Adverse Device Effect (USADE):

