8.4. Investigator Reporting Responsibilities

The investigator should report to the sponsor the following events, whether expected or not, in the corresponding CRF form, with the exception of AEs / SAEs detected before the patients has signed the patient consent form.

- AE
- SAE
- Device Deficiencies that did not but might have led to a SAE if:
 - o Suitable action has not been taken or
 - o Intervention had not been made or
 - o If circumstances had been less fortunate
- New findings/updated in relation to already reported events

If an AE / SAE is present at the beginning of study prior to the subject providing signed consent to participate in the study, only its worsening should be reported.

The investigator will document all AEs on the Adverse Event Form, including (at a minimum) a description of the event, date of onset, severity, relationship to the investigational device and/or procedure, required interventions, duration, and outcome. The investigator will monitor all AEs until they are resolved, determined to be a chronic condition or the subject is lost to follow-up. The investigator will report all AEs regardless of whether it is anticipated or unanticipated and regardless of classification, seriousness, intensity, outcome or causality.

All Serious Adverse Events including all device deficiencies that could have led to a SAE should be reported to the Sponsor within 24 hours of awareness of an event via the Adverse Event electronic Case Report Form in the study's electronic database, as that will trigger an immediate e-notification to the Sponsor and Devicia. All device deficiencies should also be reported without unjustified delay.

If the e-CRF is unavailable, notification to the sponsor can be made by email and the email address is [contact]

CLINICAL INVESTIGATION PLAN

The investigator must ensure that all additional relevant information (i.e., radiology reports, hospitalization reports indicating the SAE) that becomes available is also forwarded to the sponsor immediately after the initial notification and the information should be de-identified.

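### The data stop at withdrawal in section 6.17 conflicts with the continued safety follow-up in 5.3.4 and 8.4 for subjects taken out for harm, and leaves pregnancy outcomes uncollected

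*Combined protocol and SAP*

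**What the plan says.** Five places in the combined document bear on what is collected after a subject leaves.

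- **Section 6.17.2 (Withdrawal).** It opens with subjects who choose to leave and says "Withdrawn subjects will not undergo any additional study follow-up". It goes on to let the investigator discontinue a subject for poor compliance or "if any of the study procedures are deemed potentially harmful to the subject". After that comes "No new data will be collected after withdrawal from the study". Data gathered before the exit are kept and analysed, unless national or local rules forbid it.
- **Section 5.3.4 (Withdrawal).** It separates the exits. For discontinuation on safety grounds: "These subjects will be followed until study procedure related adverse events have resolved". For explants: "Subject who are explanted. (These subjects will be followed for six months". Attempted but uncompleted implantations also get six months, as section 5.3.3 repeats. Subjects who no longer want follow-up get none.
- **Section 8.4 (Investigator reporting).** "The investigator will monitor all AEs until they are resolved, determined to be a chronic condition or the subject is lost to follow-up". Withdrawal is not among the end points.
- **Section 6.17.3 (Unplanned pregnancy).** On pregnancy, "the pregnant subject will be withdrawn from the study", and the data stop is repeated. Section 8.1 includes among serious adverse events one that "led to foetal distress, foetal death or a congenital abnormality or birth defect".
- **Section 8, opening.** Adverse event surveillance runs from consent until participation is complete. Section 6.17.4 treats participation as complete after the 52-week visit. Neither says how an early exit is handled.

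**The concern.** Safety and durability belong to the primary objective (section 4). Subjects stopped because of harm are those in whom later adverse events, reoperation or removal of the Port are of most interest. If a site treats 6.17.2 as the governing rule, its records on such a subject end at the exit decision. If it follows 5.3.4 and 8.4, they continue. Two sites acting in good faith could therefore collect different safety data on identical subjects, and the analysis could not tell a subject with no later event from one in whom nobody was allowed to record it.

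Pregnancy raises a related problem. The plan counts foetal harm as serious, but ends data collection when the pregnancy leads to withdrawal, and most such outcomes would come after that point.

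**Working it through.** No figure in the plan quantifies this point, so the check is to compare the rules for each kind of exit and then trace the consequence into the analyses.

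**Step 1. Rules side by side**

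| Exit | Specific rule | Section 6.17 | Result |
|---|---|---|---|
| Subject declines further follow-up | 5.3.4: none | 6.17.2: none, data stop | Agree. Only 8.4 differs, for an adverse event open at exit |
| Investigator discontinues for safety | 5.3.4: until procedure-related events resolve | 6.17.2: same paragraph as the data stop | Conflict |
| Port explanted | 5.3.4: six months; 6.16.2: explant form required | 6.17.2 does not name explants, but 5.3.4 lists them as withdrawals | Conflict through the shared label |
| Implantation attempted, not completed | 5.3.3 and 5.3.4: six months | As for explants | Conflict through the shared label |
| Pregnancy | 5.3.4: not mentioned | 6.17.3: withdrawal and data stop | Gap. Conflict only for an adverse event already open (8.4) or an explant (6.16.2) |

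The second row is the firmest. The data-stop sentence comes after the sentence on harmful procedures and has no exception, so it cannot be followed together with 5.3.4 for that group.

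**Step 2. Safety proportions.** Section 10.7 reports safety as a proportion of all implanted subjects, by visit interval and as subjects with at least one event of a given type. Section 10.9 replaces no missing data.

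- With all implanted subjects as denominator N, a subject whose first event of a type falls after the data stop is missing from the numerator. The proportion drops by 1/N. If all of the minimum 200 subjects are implanted, that is 1/200 = 0.5 percentage points per such subject. The documents give no basis for the number of such subjects.
- A subject who already has a recorded event of that type stays in the numerator, because earlier data are retained. That proportion does not change.
- Section 10.9 bases percentages for categorical variables on non-missing observations. If that governs the interval tables, the subject leaves both numerator and denominator. The bias then depends on whether those removed have more later events than those who stay.

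**Step 3. Durability.** Section 10.6 censors subjects who withdraw with the device in place, and removals unrelated to device performance. Suppose a subject is discontinued for harm with the Port in place and the Port is later removed for a performance reason. Under 6.17.2 that removal is not recorded, and the subject is censored at exit. This censoring is related to the outcome and raises the estimated proportion with the Port in place.

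**The case against.** The strongest reply is that the specific text should prevail over the general. In 6.17.2 the sentence ending follow-up directly follows the one on subjects who choose to leave. The investigator sentence uses a different verb, and the heading of section 6.17 distinguishes withdrawal from discontinuation. Explants are not named in 6.17.2, and 5.3.3, 5.3.4 and 6.16.2 give clear instructions for them and for failed implantations. A sensible site would probably follow those. For explants and failed implantations this largely stands: the conflict there is one of labelling. For safety discontinuation it does not remove the problem, because the data-stop sentence comes after the investigator sentence and is unqualified.

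Several stronger readings are tempting but not supported:

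- That section 8.1 requires foetal outcomes to be followed. It is a definition and sets no follow-up duty.
- That foetal outcomes could never be captured. An adverse event already open at withdrawal falls under 8.4.
- That ending follow-up for subjects who decline it is itself inconsistent. Sections 5.3.4 and 6.17.2 agree on this.
- That subjects whose data stop are counted as event-free. Events recorded before exit are kept, someone removed for harm will often already have one, and 10.9 may show later intervals as missing. The plan leaves this open.

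Pregnancies should also be few, given the exclusion criterion on birth control and the baseline test.

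**Conclusion.** The contradiction is real for subjects discontinued on safety grounds and for adverse events open at exit. It is a matter of labelling for explanted and failed-implantation subjects. For pregnancy it is mainly a gap in what is captured. If sites apply 6.17 as written, later safety outcomes and explants are lost in subjects removed for harm. That can bias the safety proportions and the durability estimate in the device's favour.

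The size cannot be derived from the documents, which give neither the number of such exits nor the rate of later events. The direction rests on three assumptions: some sites let 6.17 override 5.3.4 and 8.4; at least some lost events are the subject's first of that type, or some lost removals are performance-related; and subjects removed for harm have at least as many later events as the rest. A reader might infer a shift of several percentage points in the safety rates, but any such figure would be built from invented rates and would ignore the retained earlier events. The case for amending does not depend on it, because the sections cannot all be followed as they stand.

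**What to change.** Reconcile sections 5.3.4, 6.17.2, 6.17.3, the opening of section 8, and 8.4 so that each exit category has one data-collection rule:

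- Limit the end of study follow-up and the data stop to subjects who decline further follow-up, and state in 8.4 how an adverse event open at that moment is closed in the database.
- For investigator discontinuation, explantation and uncompleted implantation, keep the safety data collection that 5.3.4 and 8.4 already describe, including the explant form under 6.16.2.
- For pregnancy, state that the outcome is recorded as safety data where the subject consents.
- In the opening of section 8, say when adverse event surveillance ends for each exit.

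The statistical analysis plan should also say whether subjects without data in an interval stay in the safety denominator.

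The cost is protocol wording and a few additional records, since most of the follow-up is already foreseen. This concerns data collection only; it takes no position on how any of these subjects should be managed clinically.

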3. STUDY DESIGN

This is a multi-center, open study that evaluates the safety, performance and durability of the TIES® transcutaneous titanium implant to 12-months post implantation.

This study will be conducted in accordance with the Standard ISO 14155 and other legal requirements.

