10.3. Study Population Definition

The study population is defined according to the Intent-to-Treat principle. All enrolled subjects will be taken into consideration in the reported results, without any planned exclusion.

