10.4. Performance Evaluation

The subject is assumed to empty the “bowels” about 6 times per day. 6-months is chosen as the time point for primary endpoint assessment because the subject is expected to be familiar with the use of the TIES® Lid as well as study procedures at that time.

- By analysing the frequency of use of the TIES® Lid versus the use of stoma bags in individual subjects, this gives an assessment of the usefulness and acceptability of the TIES® solution.
- Leakage around the stoma between emptying is to be assessed. For a conventional end-ileostomy, the peristomal skin is often in contact with the intestinal contents and at least 30% of the patients reported skin problems based on the literature. For patients with pelvic pouch, perfect continence is achieved in less than 80% of patients.

Performance evaluation is based on subject's assessment of performance as recorded on the 3-day diary preceding each scheduled follow-up at 16, 24, 36 and 52 weeks after

CLINICAL INVESTIGATION PLAN

operation. Performance evaluation applies only among subjects with the TIES® Port *in situ*.

Among subjects with the TIES® Port *in situ*, performance will be assessed according to (a) the proportion of subjects who use the TIES® Lid for continence control; (b) the proportion of subjects experiencing visible leakages around the implant; and (c) subject's assessment on the ease of use of the TIES® Solution.

Primary endpoint is absence of visible leakage or fecal staining of clothing at 24 weeks after implantation of the TIES® Port.

The success criterion at 24 weeks requires at least 70% of subjects with the TIES® Port *in situ* having no visible leakage or staining of clothing adjacent to the implant between consecutive episodes of using the lid for continence control. Spillage that might occur at opening of the lid is not regarded as leakage.

Secondary endpoints are

- Absence of visible leakage or fecal staining of clothing at 16, 36 and 52 weeks.
- Proportion of implanted subjects using the TIES® Lid for continence control at 16, 24, 36 and 52 weeks.
- Subject's assessment on the ease of use of the TIES® Lid using a visual analog scale 16, 24, 36 and 52 weeks after implantation.
- Subject's preference for the TIES® solution assessed at 52 weeks.

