11.3. Protocol Deviations

The Principal Investigator is required to conduct the study in accordance with the signed clinical trial agreement/investigator agreement and the clinical protocol. However in some situations protocol deviations will occur.

Protocol deviations are defined as instance(s) of failure to follow, intentionally or unintentionally, the requirements of the CIP. Under emergency circumstances, deviations from the CIP to protect the rights, safety and well-being of human subjects may proceed without prior approval of the sponsor and the EC. Such deviations shall be documented and reported to the sponsor and the EC as soon as possible.

The Principal Investigator shall promptly report any deviations from the CIP that affects the rights, safety or well-being of the subject or the scientific integrity of the clinical investigation, including those which occur under emergency circumstances. The Principal Investigator shall notify the Sponsor in writing, no later than 24 hours after significant deviation from the study plan, to protect the life or physical wellbeing of a subject in an emergency.

When specific tasks are delegated by the Principal Investigator, included but not limited to conducting the informed consent process, the Principal Investigator is responsible for providing appropriate training and adequate supervision of those to whom tasks are delegated. The investigator is accountable for regulatory deviations resulting from failure to adequately supervise the conduct of the clinical study.

Protocol deviations also include, but are not limited to:

- Examinations/test/assessment not performed within the allowed follow-up window
- Required data not obtained

The study site should report the protocol deviation on the applicable CRF page.

Protocol deviations will be reported in progress reports to CA and EC where applicable and within other required timelines.

Investigators that show continued, serious failings in adherence to the CIP, inspite of appropriate corrective and preventive actions will be disqualified from the study.

CLINICAL INVESTIGATION PLAN

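### Section 6.17.2 lets the open-label investigator end participation for poor compliance without criteria, so a subject discontinued before week 24 drops out of the primary proportion and is censored in durability.

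*Combined protocol and SAP*

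**What the plan says.** - **Grounds for exit.** Section 6.17.2 gives the investigator two grounds for discontinuing a subject. One is study procedures judged potentially harmful. The other applies "if the investigator feels that the subject can no longer fully comply with the requirements of the study". No threshold, documentation standard or sponsor review is attached to the second. Section 5.3.4 lists five reasons for early exit, and the only investigator-initiated one reads "Investigator believes it is the best medical interest of the subject to discontinue study participation due to safety reasons".
- **After exit.** Section 6.17.2 says "Withdrawn subjects will not undergo any additional study follow-up" and "No new data will be collected after withdrawal from the study". Section 5.3.4 does not replace withdrawn subjects. For investigator safety exits it keeps follow-up going until procedure-related events resolve, which also differs from 6.17.2.
- **Design.** Section 3: "This is a multi-center, open study". Section 10.1 adds that it is single-arm.
- **Primary endpoint.** Section 10.4: "Performance evaluation applies only among subjects with the TIES® Port" in situ, and it rests on the three-day diary before the visit. Section 10.9 does not replace missing data and computes percentages on non-missing observations.
- **Durability.** Section 10.6 censors subjects who withdraw with the device in situ.
- **Population.** Section 10.3: "All enrolled subjects will be taken into consideration in the reported results, without any planned exclusion".
- **Deviations.** Section 11.3 already classes as deviations required data not obtained and "Examinations/test/assessment not performed within the allowed follow-up window".

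**The concern.** Completing diaries and attending visits are study requirements, and they are also the source of the primary outcome. A subject whose Port leaks or is hard to manage may well be the one who falls behind on them. The investigator examines the stoma at each visit and knows how the device is performing. The plan therefore lets a person who knows the likely outcome decide, on a subjective basis, that no outcome will be recorded.

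With no control arm, there is no parallel loss that might offset the bias. By contrast, loss to follow-up in section 6.17.1 requires three missed consecutive visits, three documented contact attempts and a report to the sponsor. The compliance exit has no comparable safeguard.

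At stake are the single primary success criterion and the durability estimate, both of which move in the device's favour if leaking subjects are discontinued more often than others.

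**Working it through.** **1. What happens to such a subject.** Suppose discontinuation comes before week 24 with the Port in place. No data follow (6.17.2), so there is no 24-week diary (10.4). The value is not replaced, and the percentage uses non-missing values (10.9). The subject is in neither numerator nor denominator of the primary proportion. In durability the subject is censored (10.6); section 6.17.2 treats investigator discontinuation under its Withdrawal heading, so the censoring rule reaches it. Section 10.3 is not carried into any rule for counting a subject without a 24-week diary.

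**2. The plan's own figure.** Section 10.5 tabulates the power for a lower two-sided 95% limit of at least 60%. Power = Φ((p − 0.60)/√(p(1−p)/n) − 1.96). For p = 0.70 and n = 160: √(0.21/160) = 0.0362; 0.10/0.0362 = 2.76; Φ(0.80) = 78.8%, against the stated 79%. All 30 cells agree within 0.5 point. The calculation treats assessable subjects as representative of all subjects.

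**3. How few removals matter.** Take 160 evaluable subjects (80% of 200, section 10.5), x of them leak-free. Remove k leaking subjects and recompute x/(160 − k). The exact (Clopper-Pearson) lower limit is the 2.5% quantile of Beta(x, n − x + 1). For the 70% criterion of section 10.4, taken as a point estimate, k is the smallest integer with 160 − k ≤ x/0.70.

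| Leak-free of 160 | Exact lower limit at 160 | Removals to reach lower limit 60% (10.5) | Removals to reach 70% (10.4) |
|---|---|---|---|
| 103 (64.4%) | 56.4% | 9 | 13 |
| 104 (65.0%) | 57.1% | 8 | 12 |
| 105 (65.6%) | 57.7% | 6 | 10 |
| 106 (66.3%) | 58.4% | 4 | 9 |
| 107 (66.9%) | 59.0% | 3 | 8 |
| 108 (67.5%) | 59.7% | 1 | 6 |
| 110 (68.8%) | 61.0% | already met | 3 |

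For 106: 106/157 has limit 59.6% and 106/156 has 60.01%. The Wilson limit also crosses at four (60.3%). The Wald limit, which matches the plan's table, crosses at three (106/157, 60.2%). For the 70% criterion: 106/0.70 = 151.4, so 106/151 = 70.2% after nine removals; 110/0.70 = 157.1, so 110/157 = 70.1% after three.

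**4. Effect on the chance of success.** Assume each leaking subject is discontinued before week 24 with probability q and leak-free subjects never are. The documents give no value for q. The expected observed proportion is p/(1 − (1 − p)q). Exact binomial enumeration with 160 subjects and the Wald limit gives:

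| True leak-free | q | Observed | Chance lower limit ≥ 60% |
|---|---|---|---|
| 60% | 0 / 10 / 20 / 30% | 60.0 / 62.5 / 65.2 / 68.2% | 3.1 / 10.3 / 27.8 / 55.1% |
| 65% | 0 / 10 / 20 / 30% | 65.0 / 67.4 / 69.9 / 72.6% | 28 / 50 / 74 / 91% |

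Counting the discontinued subjects as failures restores the q = 0 values.

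**5. Durability.** Assume 200 subjects, true in-situ proportion 80% at 52 weeks, and a quarter of the 40 who would lose the Port censored early. The estimate is 1 − 30/190 = 84.2%. With a tenth it is 1 − 36/196 = 81.6%; with half, 1 − 20/180 = 88.9%.

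**The case against.** Several points on the other side are sound and limit the claim.

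- **Lid use is not shown to be a requirement.** A reader might infer that subjects who struggle with the Lid can be removed as non-compliant. The plan does not define the study's requirements. Section 7.1.3.3 calls for Lid use to be paused when ingrowth is incomplete, section 10.4 treats Lid versus bag use as an outcome, and section 10.10.2 expects continued bag use during sleep. What stands is the narrower route through diaries and visits.
- **Section 5.3.4 is not exhaustive.** It also omits loss to follow-up (6.17.1) and pregnancy (6.17.3). The mismatch is a reason to reconcile the sections, not proof that 6.17.2 breaches a closed list. The selection risk does not depend on the list.
- **Section 10.3 is not directly contradicted.** Section 6.17.2 keeps data already collected for analysis, so the subject remains in the population. The gap is the missing counting rule.
- **The same denominator and censoring rules apply to voluntary withdrawal and to missed diaries.** This is correct, and it means that deleting a clause cannot be the whole remedy: a retained subject with no diary is still missing.
- **There is partial handling.** Reasons for withdrawal are recorded if given, and section 10.9 promises a full analysis plan before analysis. Neither says how these subjects count.

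**Conclusion.** The point holds as a design weakness of moderate importance. The plan permits discontinuation by someone aware of the outcome on an undefined compliance ground, stops data collection at that moment, and has no rule that detects or neutralises the effect on the primary proportion or on durability.

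A reader might take the four-removal example (4/160 = 2.5% of subjects) as showing that the trial's result would be reversed. The documents do not support that. It holds only under the lower-limit rule of section 10.5 and for a count near the boundary; 106/156 is 67.9%, which still misses the 70% criterion of section 10.4. Depending on the starting count, the section 10.5 rule needs from one removal (108) to nine (103).

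The size rests on two assumptions: that leaking subjects are discontinued more often than others, and the assumed rate q. The documents give no information on how often the clause would be used. Nothing in them suggests intended misuse.

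**What to change.** 1. Reconcile sections 5.3.4 and 6.17.2, including their different follow-up after investigator discontinuation, and remove non-compliance as a reason to end study participation.
2. State that missed diaries or visits are recorded as deviations under section 11.3, and that Port status, leakage and adverse events continue to be collected at the remaining visits unless the subject withdraws consent.
3. Record every investigator discontinuation by reason and report the counts.
4. Because retention alone does not restore a missing diary, add two sensitivity analyses. For the primary endpoint, count subjects discontinued with the Port in situ and no 24-week diary as failures. For durability, count subjects discontinued with the Port in situ as events instead of censoring them.

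The cost is a few sentences in the protocol and analysis plan, some visits with incomplete data, and a slightly less favourable sensitivity estimate. Treatment is unchanged, and the subject's own right to withdraw is untouched.
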